**Table 1 Classifications (cont.)**

Class	Description
Class V	Membranous LN Global or segmental subepithelial immune deposits or their morphologic sequelae by light microscopy and by immunofluorescence or electron microscopy, with or without mesangial alterations Class V LN may occur in combination with class III or IV in which case both will be diagnosed. Class V LN may show advanced sclerosis
Class VI	Advanced sclerotic LN ≥90% of glomeruli globally sclerosed without residual activity

A=active; C=chronic; G=global; LN=lupus nephritis; S=segmental.

**Table 2 Definitions**

Term	Definition
Diffuse	A lesion involving most ( $\geq 50\%$ ) glomeruli
Focal	A lesion involving $< 50\%$ of glomeruli
Global	A lesion involving more than half of the glomerular tuft
Segmental	A lesion involving less than half of the glomerular tuft (i.e., at least half of the glomerular tuft is spared)
Mesangial hypercellularity	At least three mesangial cells per mesangial region in a 3 micron thick section
Endocapillary proliferation	Endocapillary hypercellularity due to increased number of mesangial cells, endothelial cells, and infiltrating monocytes, and causing narrowing of the glomerular capillary lumina
Extracapillary proliferation or cellular crescent	Extracapillary cell proliferation of more than two cell layers occupying one fourth or more of the glomerular capsular circumference
Karyorrhexis	Presence of apoptotic, pyknotic, and fragmented nuclei
Necrosis	A lesion characterized by fragmentation of nuclei or disruption of the glomerular basement membrane, often associated with the presence of fibrin-rich material
Hyaline thrombi	Intracapillary eosinophilic material of a homogeneous consistency by which immunofluorescence has been shown to consist of immune deposits
Proportion of involved glomeruli	Intended to indicate the percentage of total glomeruli affected by LN, including the glomeruli that are sclerosed due to LN, but excluding ischemic glomeruli with inadequate perfusion due to vascular pathology separate from LN

LN = lupus nephritis.

Source: Weening JJ, D'Agati VD, Schwartz MM, et al. The classification of glomerulonephritis in systemic lupus erythematosus revisited. *J Am Soc Nephrol* 2004;15:241–50.

**Appendix 3 International Society of Nephrology/Renal Pathology Society (ISN/RPS)  
2003 Classification of Lupus Nephritis (cont.)**

**DEFINITION OF ACTIVE AND CHRONIC LESIONS**

**Active Lesions**

- Endocapillary hypercellularity with or without leukocyte infiltration and with substantial luminal reduction
- Karyorrhexis
- Fibrinoid necrosis
- Rupture of glomerular basement membrane
- Crescents, cellular or fibrocellular subendothelial deposits identifiable by light microscopy (wireloops)
- Intraluminal immune aggregates (hyaline thrombi)

**Chronic Lesions**

- Glomerular sclerosis (segmental, global)
- Fibrous adhesions
- Fibrous crescents

## Appendix 4

### Guidelines for Mycophenolate Mofetil (or Equivalent) Dosing

#### **INITIAL DOSING**

Patients may use either mycophenolate mofetil (MMF) or mycophenolic acid (MPA) as standard of care background therapy in this study. Dosing guidelines are based on use of MMF but an equivalent dose of MPA may be used (MMF 500 mg is equivalent to MPA 360 mg). Patients should be initiated on MMF at a dosage of 1500 mg/day (or equivalent) in divided doses. The target MMF dosage for the protocol is 2000 to 2500 mg/day (or equivalent).

If patients are already receiving MMF (or equivalent) upon entry into the study, their current dosage should be  $\geq$  1500 mg/day (or equivalent); if the dosage is not  $\geq$  1500 mg/day (or equivalent), then it should be increased to that level. The patient's dose should also be divided into two or three times-a-day dosing.

#### **ESCALATION OF DOSE**

The dosage of MMF (or equivalent) should be increased, as tolerated, by 500 mg/week (or equivalent) with the goal of reaching 2000–2500 mg/day (or equivalent), given in divided doses, by Week 4 at the latest.

#### **ADJUSTMENTS TO MMF (OR EQUIVALENT) DOSE**

Investigators will be allowed to adjust the dosage because of tolerance and adverse effects, but the dosage should not be increased to greater than 2500 mg/day (or equivalent). The most common adverse effects requiring titration of MMF (or equivalent) are gastrointestinal (GI) intolerance, neutropenia, and infectious complications (CellCept® U.S. Package Insert [USPI], Myfortic® USPI). To maintain consistency in dose adjustments, recommended reductions are listed in [Table 1](#).

If a patient develops GI toxicity due to MMF (or equivalent), it is recommended to reduce the dose according to “step 1,” as listed in [Table 1](#) if other methods/evaluations, as outlined below, are not helpful. If symptoms persist for 2 weeks after the change, the investigator may reduce the dose according to “step 2,” as listed in [Table 1](#). After the symptoms resolve, an attempt should be made to increase MMF (or equivalent) to a goal of 2000 mg/day (or equivalent) per the previous dosing algorithm. If GI symptoms return, then the patient should be continued on the highest tolerable dose.

GI toxicity may not necessarily require dose reduction of MMF (or equivalent). If diarrhea occurs, infectious causes (e.g., *C. difficile* and enteropathogens) should be ruled out and treated if necessary. If, in the investigator's opinion, the diarrhea is non-infectious, agents such as Lomotil® or tincture of opium may be used to decrease diarrhea.

## **Appendix 4** **Guidelines for Mycophenolate Mofetil (or Equivalent) Dosing** **(cont.)**

If a patient develops an absolute neutrophil count (ANC) between 1000 and 1200, the dose should be reduced according to “step 1,” as listed in [Table 1](#) and the neutrophil count should be checked again at the next scheduled visit. If the ANC continues to be between 1000 and 1200, the dose should be reduced according to “step 2,” as listed in [Table 1](#). After the ANC increases to  $> 1200$ , the dose should be titrated towards goal, but at a rate of 500 mg per month.

If the patient’s ANC is  $< 1000$ , MMF (or equivalent) must be stopped immediately. The patient must return within 14–21 days for repeat measurement of ANC. If ANC is  $> 1500$ , then MMF (or equivalent) may be restarted at the “step 1” dose according to what the patient’s previous MMF (or equivalent) dose was. For example, if the patient’s dosage of MMF was 2500 mg/day at the time of interruption of MMF, then MMF should be restarted at 2000 mg/day.

If a patient experiences an infectious complication, MMF (or equivalent) should be stopped until the episode has resolved. MMF (or equivalent) can then be reinstated at the previous dose.

Regardless of dose reduction, every attempt must be made to bring the patient’s dosage of MMF (or equivalent) to  $\geq 1500$  mg/day (or equivalent).

**Table 1 Protocol-Specified MMF (or Equivalent) Dose Reduction**

MMF dosage (mg/day)	Step 1 Reduction (mg)	Step 2 Reduction (mg)
2500	2000	1500
2250	1750	1250
2000	1500	1000
1500	1000	750

### Initial Prednisone/Prednisolone Tapering Schedule

Patients will receive both intravenous (IV) and oral corticosteroids as part of their initial course of therapy. IV methylprednisolone will be dosed at 1000 mg to treat active lupus nephritis (LN) according to standard clinical practice, which typically recommends one to three infusions of methylprednisolone at this dose. Between one and three infusions of 1000 mg methylprednisolone will be allowed for the inclusion of patients into this protocol and can occur at any time before or during the screening interval. For instance, a patient with LN may have been identified in the community prior to referral to the investigator's site and received 1000 mg of methylprednisolone. This dose and all doses of steroids must be accounted for in the steroid concomitant medications section of the case report form. The target protocol methylprednisolone dose is a single 1000 mg infusion, but up to three infusions will be acceptable for study entry.

The initial oral prednisone dose will be 0.50 mg/kg/day, not to exceed 60 mg, and will be given on Days 2–16, excluding concomitant dosing of IV methylprednisolone.

Investigators are instructed to round the calculated dose to the nearest 10-mg increment listed in [Table 1](#). The investigator should instruct the patient to initiate a corticosteroid taper beginning on Day 16. The patient's initial study prednisone dose (or equivalent) is listed on the top line of [Table 1](#), and the subsequent doses, changing every 2 weeks, are noted in the column below the selected initial dose. Patients whose calculated prednisone dose would be >60mg/day should use 60 mg/day as their starting dose.

**Table 1 Prednisone Tapering Schedule**

Starting Prednisone Dose (mg/day)	30	40	50	60
Day 16	25	35	40	50
Day 28	25	30	30	40
Day 42	20	25	20	30
Day 56	15	20	15	20
Day 70	10	15	10	10
Day 84	7.5	7.5	7.5	7.5

#### **CORTICOSTEROID DOSING FOR EXTRARENAL FLARES**

To maintain consistency in the use of corticosteroids for extrarenal flares, patients will not be allowed to increase their prednisone dose during their participation in the study unless it is judged clinically appropriate by the investigator. A flare is defined as an increase in Systemic Lupus Erythematosus Disease Activity Index (SLEDAI)-2K that is not accounted for by either hypocomplementemia or an increase in anti-dsDNA antibody level or the initiation of new immunosuppressive therapy or an increase of corticosteroid

## Appendix 5

### Initial Prednisone/Prednisolone Tapering Schedule (cont.)

dose. On the basis of the severity of the disease, patients may be retreated with prednisone up to 1.0 mg/kg. IV corticosteroids in equivalent doses may be allowed if gastrointestinal involvement temporarily precludes oral corticosteroid use.

Because it is important to maintain a consistent corticosteroid taper to interpret the results of this clinical study, it is suggested that investigators round the calculated corticosteroid dose (based on the patient's weight in kilograms) to the nearest 10-mg increment listed in [Table 2](#) (not to exceed 60 mg/day) and follow the recommended tapering schedule. The investigator should instruct the patient to initiate a corticosteroid taper 14 days after starting the increased corticosteroid dose. The patient's increased study prednisone dosage (or equivalent) is listed on the top line of [Table 2](#), and the subsequent dosages, changing every 2 weeks, are noted in the column below the selected initial dose. If the investigator determines that a higher dose or longer treatment period is necessary, he or she should first contact the Medical Monitor to discuss this. Patients who do not show improvement in their symptoms after 2 weeks of increased corticosteroid treatment are considered to be nonresponsive to corticosteroids.

Patients who initiate a new immunosuppressive or any other new systemic lupus erythematosus medication will return for all protocol-scheduled visits and will not receive further study drug.

**Table 2 Prednisone Dosing Recommendations for Extrarenal Flares**

Starting Prednisone Dose (mg/day)	20	30	40	50	60
Day 16	15	25	30	40	50
Day 30	10	20	25	30	40
Day 44	10	10	15	20	30
Day 58	7.5	10	10	10	20
Day 72	7.5	7.5	10	10	10
Day 86	7.5	7.5	7.5	7.5	7.5

### **CORTICOSTEROID DOSING FOR RENAL FLARES**

To maintain consistency in the treatment of renal flares, retreatment with higher doses of corticosteroids is permitted if judged clinically appropriate by the investigator and if patients meet the criteria for a renal flare as defined by all of the following:

- Stable or increased creatinine

## Appendix 5

### Initial Prednisone/Prednisolone Tapering Schedule (cont.)

- Worsening active urinary sediment from baseline, as defined by a  $\geq 50\%$  increase in RBCs/high-power field or the appearance of new RBC casts when none were previously present
- Increase in proteinuria, as evidenced by an increase in the urine protein to creatinine ratio to  $> 2$ , if the most recent urine protein to creatinine ratio was  $< 2$ .

Patients may be treated with prednisone (up to 0.5 mg/kg; not to exceed 60 mg/day) for 2 weeks. Prednisone will then be tapered to achieve  $\leq 10$  mg/day 6 weeks after the initial corticosteroid increase (see [Table 3](#)). Patients who do not exhibit a response to the initial 2 week course of increased corticosteroids, as evidenced by an improvement in urinary sediment and/or a reduction in the urine protein to creatinine ratio, or who initiate a new immunosuppressive therapy will be deemed treatment failures and continue scheduled protocol visits of the study and will not receive additional study drug.

**Table 3 Prednisone Dosing Recommendations for Renal Flares**

Days after Initial Corticosteroid Increase	Prednisone Dose (mg/day)				
	20	30	40	50	60
14	15	25	30	40	50
21	15	20	25	30	40
28	10	20	20	20	30
35	10	15	15	15	20
42	10	10	10	10	10

## **Appendix 6** **Criteria for Classification of Systemic Lupus Erythematosus**

There are 11 criteria for the classification of systemic lupus erythematosus (SLE). On the basis of this classification, a patient would be considered to have “definite” SLE if any 4 or more of the 11 criteria are present, serially or simultaneously, during any interval of observation.

In this study, a patient will be considered to have SLE if he or she has at least four criteria present, one of which must be a positive anti-nuclear antibody (Criterion 11).

Criterion	Definition
1. Malar rash	Fixed erythema, flat or raised, over the malar eminences, tending to spare the nasolabial folds
2. Discoid rash	Erythematous raised patches with adherent keratotic scaling and follicular plugging; atrophic scarring may occur in older lesions
3. Photosensitivity	Skin rash as a result of unusual reaction to sunlight, by patient history or physician observation
4. Oral ulcers	Oral or nasopharyngeal ulceration, usually painless, observed by physician
5. Arthritis	Nonerosive arthritis involving $\geq 2$ peripheral joints, characterized by tenderness, swelling, or effusion
6. Serositis	a) Pleuritis--convincing history of pleuritic pain or rubbing heard by a physician or evidence of pleural effusion OR b) Pericarditis--documented by ECG or rub or evidence of pericardial effusion
7. Renal disorder	a) Persistent proteinuria $>0.5$ g/day or $>3+$ if quantitation not performed OR b) Cellular casts--may be red cell, hemoglobin, granular, tubular, or mixed
8. Neurologic disorder	a) Seizures--in the absence of offending drugs or known metabolic derangements (e.g., uremia, ketoacidosis, or electrolyte imbalance) OR b) Psychosis--in the absence of offending drugs or known metabolic derangements (e.g., uremia, ketoacidosis, or electrolyte imbalance)

**Appendix 6**  
**Criteria for Classification of Systemic Lupus Erythematosus**  
**(cont.)**

Criterion	Definition
9. Hematologic disorder	a) Hemolytic anemia--with reticulocytosis OR b) Leukopenia: $<4,000/\text{mm}^3$ total on 2 or more occasions OR c) Lymphopenia: $<1,500/\text{mm}^3$ on 2 or more occasions OR d) Thrombocytopenia: $<100,000/\text{mm}^3$ in the absence of offending drugs
10. Immunologic disorder a	a) Anti-DNA: antibody to native DNA in abnormal titer OR b) Anti-SM: presence of antibody to SM nuclear antigen OR c) Positive finding of antiphospholipid antibodies based on (1) an abnormal serum level of IgG or IgM anti-cardiolipin antibodies, (2) a positive test result for lupus anticoagulant using a standard method, or (3) a false positive serologic test for syphilis known to be positive for $\geq 6$ months and confirmed by Treponema pallidum immobilization or fluorescent treponemal antibody absorption test
11. Anti-nuclear antibody	An abnormal titer of anti-nuclear antibody by immunofluorescence or an equivalent assay at any point in time and in the absence of drugs known to be associated with "drug-induced lupus" syndrome

a The modifications to criterion number 10 were made in 1997 (Hochberg 1997).

Source: Tan et al. 1982.

### Study Drug Administration

#### **ADMINISTRATION OF STUDY DRUG**

Study drug (obinutuzumab or placebo) should be given as a slow intravenous (IV) infusion. It should not be administered as an IV push or bolus.

Although obinutuzumab may be administered on an outpatient basis, patients may be hospitalized for observation at the discretion of the investigator. Irrespective, obinutuzumab must be administered in a hospital or clinic environment where full resuscitation facilities are immediately available and under close supervision of the investigator or designee. The guidelines below may be slowed at the discretion of the investigator based on a patient's clinical presentation.

#### **FIRST INFUSION (DAY 1)**

Patients should receive prophylactic treatment of acetaminophen (650–1000 mg) and diphenhydramine hydrochloride (HCl) (50 mg; or equivalent dose of a similar agent) by mouth 30–60 minutes prior to the start of an infusion. Prior to the Day 1 infusion, patients must receive 80 mg IV methylprednisolone or placebo 30–60 minutes prior to the start of the study drug infusion.

NOTE: Patients should be cautioned not to operate vehicles or hazardous machinery until their response to diphenhydramine (or similar antihistamine) has been determined.

Study drug infusions should be made through a dedicated line and commence at a rate of 50 mg/hr. This may be escalated at a rate of 50 mg/hr every 30 minutes to a maximum of 400 mg/hr. [Table 1](#) presents the schedule for the first infusion.

**Table 1 Schedule for First Infusion**

Time (min)	Infusion Rate		Dose in 30 minutes (mg)	Cumulative Dose (mg)
	(mg/hr)	(mL/hr)		
0–30	50	12.5	25	25
31–60	100	25	50	75
61–90	150	37.5	75	150
91–120	200	50	100	250
121–150	250	62.5	125	375
151–180	300	75	150	525
181–210	350	87.5	175	700
212–240	400	100	200	900
241–255 a	400	100	200	1000

a Should complete at 255 minutes (4 hours, 15 minutes) to complete total dose of 1000 mg.

## **Appendix 7** **Study Drug Administration (cont.)**

If a patient experiences a mild infusion-related reaction (IRR) that is deemed by the investigator to be clinically significant, the infusion rate should be reduced to half the infusion rate that was used at the time of the reaction (e.g., from 100 mg/hr to 50 mg/hr). After the reaction has resolved, the infusion should be kept at the reduced rate for an additional 30 minutes. If the reduced rate is tolerated, then the infusion rate may be increased to the next closest rate on the infusion schedule. Patients who experience a moderate-to-severe IRR should have their infusion interrupted immediately and should receive aggressive symptomatic treatment. The infusion should not be restarted before all the symptoms have disappeared; after all symptoms have disappeared, the infusion may be restarted at half the rate. If the reduced rate is tolerated for 30 minutes, then the infusion rate may be increased to the next closest rate on the infusion table.

After the end of the first infusion, the IV line should remain in situ for at least 2 hours to be able to administer drugs intravenously if necessary. At the end of the remaining infusions, the IV line should remain in place for at least 30 minutes. If no adverse events occur during this period of time, the IV line may be removed.

### **SUBSEQUENT INFUSIONS (DAYS 15, 168, AND 182)**

Patients should receive prophylactic treatment of acetaminophen (650–1000 mg) and diphenhydramine HCl (50 mg; or equivalent dose of similar agent) by mouth 30–60 minutes prior to the start of an infusion. Patients must receive 80 mg IV methylprednisolone or placebo 30–60 minutes prior to the start of the study drug infusion.

Patients who tolerated the first infusion of study drug well may receive the second infusion as detailed in [Table 2](#). Patients who experienced an IRR to the first infusion, deemed by the investigator to be clinically significant, should receive study drug as per the initial infusion schedule, with the starting rate of infusion not exceeding half that associated with the prior reactions. If the infusion reaction during the first infusion occurred at a rate >200 mg/hr, then the second infusion rate should start at 100 mg/hr.

Study drug infusions should be made through a dedicated line and commence at a rate of 100 mg/hr. This may be escalated at a rate of 100 mg/hr every 30 minutes to a maximum of 400 mg/hr. [Table 2](#) presents the schedule for the second and subsequent infusions.

In the event that the patient experiences an IRR, the infusion rate should be reduced to half that rate (e.g., from 100 mg/hr to 50 mg/hr). Patients who experience a moderate-to-severe IRR should have their infusion interrupted immediately and should receive aggressive symptomatic treatment. The infusion should not be restarted before all the symptoms have disappeared (see above).

## Appendix 7

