#### **Obinutuzumab Administration**

Obinutuzumab should be administered to patients in a clinical setting (inpatient or outpatient) where full emergency resuscitation facilities are immediately available and patients should be under close supervision of the investigator at all times. Do not

administer as an IV push or bolus. After the end of the first infusion, the IV line should remain in place for  $\geq$  2 hours in order to be able to administer IV drugs if necessary. If no adverse events occur after 2 hours, the IV line may be removed. For subsequent infusions, access through an IV line should remain in place for at least 30 minutes from the end of the infusion, and if no adverse events occur after 30 minutes, the IV access may be removed.

Patients should receive prophylactic treatment with acetaminophen (650–1000 mg) and diphenhydramine (50 mg; or equivalent dose of a similar agent) by mouth 30–60 minutes prior to the study drug infusion. Methylprednisolone 80 mg IV must be given 30–60 minutes prior to the start of infusions on Days 1, 15, 168, and 182.

Patients who are administered an antihistamine (e.g., diphenhydramine) for the treatment or prevention of IRRs should be given appropriate warnings prior to the patients' discharge about drowsiness and impairment of ability to drive.

Instructions for administration of obinutuzumab infusions are provided in [Table 2](#) and [Appendix 7](#).

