**Table 2 Administration of Obinutuzumab Infusions**

First Infusion (Day 1)	Subsequent Infusions (Days 15, 168, and 182)
Begin infusion at an initial rate of 50 mg/hr. If no infusion reaction occurs, increase the infusion rate in 50-mg/hr increments every 30 minutes to a maximum of 400 mg/hr. If an infusion reaction develops, stop or slow the infusion. Administer infusion-reaction medications and supportive care in accordance with institutional protocol. Resume the infusion at a 50% reduction in rate (the rate being used at the time that the hypersensitivity or IRR occurred) if the reaction has resolved.	If a patient experienced an infusion reaction during the prior infusion, start at the same rate as the first infusion (50 mg/hr) and follow those directions as noted. If the patient tolerated the prior infusion well, begin infusion at a rate of 100 mg/hr. If no infusion reaction occurs, increase the infusion rate in 100-mg/hr increments every 30 minutes to a maximum of 400 mg/hr. If an infusion reaction develops, stop or slow the infusion. Administer infusion-reaction medications and supportive care in accordance with institutional protocol. Resume the infusion at a 50% reduction in rate (the rate being used at the time that the hypersensitivity or IRR occurred) if the reaction has resolved.

IRR=infusion-related reaction.

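### After a first-infusion reaction above 200 mg/hr, main-body Table 2 and Appendix 7 give different default starting rates for the second infusion (50 and 100 mg/hr), and neither is said to prevail

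*Protocol*

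**What the plan says.** Section 4.3.2.1, under Obinutuzumab Administration, points the site to two sources: "Instructions for administration of obinutuzumab infusions are provided in" main-body Table 2 and Appendix 7. It does not say which applies if they differ.

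Main-body Table 2, for Days 15, 168 and 182, says: "If a patient experienced an infusion reaction during the prior infusion, start at the same rate as the first infusion (50 mg/hr". The rule applies to any reaction at the prior infusion, whatever the rate at which it occurred. Patients who tolerated the prior infusion start at 100 mg/hr.

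Appendix 7, under Subsequent Infusions, is more detailed. A patient with a clinically significant reaction at the first infusion goes back to the initial schedule, "with the starting rate of infusion not exceeding half that associated with the prior reactions". If that reaction occurred above 200 mg/hr, "then the second infusion rate should start at 100 mg/hr". The next paragraph says that study drug infusions "commence at a rate of 100 mg/hr" and does not limit this to patients who tolerated the earlier infusion.

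Appendix 7 also opens with a general clause that its guidelines "may be slowed at the discretion of the investigator".

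**The concern.** A patient with a clinically significant first-infusion reaction at 250 mg/hr or more meets both triggers, so two written defaults apply to the same Day 15 infusion. Which one is used depends on the page the site read. These patients have already reacted once, and infusion-related reactions are an adverse event of special interest (Section 5.2.3). Section 9.2 requires deviations to be documented, yet a site that follows Appendix 7 literally departs from main-body Table 2, and nothing says whether that counts as a deviation.

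The overlap is narrow. The 100 mg/hr sentence concerns only the second infusion, and only reactions above 200 mg/hr at the first.

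**Working it through.** **Inputs**
- Start after a reaction, main-body Table 2: 50 mg/hr, then the first-infusion steps.
- Start after a first-infusion reaction above 200 mg/hr, Appendix 7: 100 mg/hr.
- Half-rate cap on the start, Appendix 7.
- First-infusion schedule (main-body Table 2; Appendix 7, Table 1): steps of +50 mg/hr every 30 minutes, maximum 400 mg/hr, total 1000 mg.

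**Formula.** Dose per 30-minute step = rate × 0.5 h. Total time = 30 minutes × full steps + (remaining dose ÷ 400) × 60 minutes.

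**Check against the protocol's own figure (start at 50 mg/hr).** 25 + 50 + 75 + 100 + 125 + 150 + 175 + 200 = 900 mg at 240 minutes. The remaining 100 mg takes 100 ÷ 400 × 60 = 15 minutes. The total is 255 minutes, as Appendix 7 Table 1 states.

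**Same schedule entered at 100 mg/hr.** 50 + 75 + 100 + 125 + 150 + 175 + 200 = 875 mg at 210 minutes. The remaining 125 mg takes 125 ÷ 400 × 60 = 18.75 minutes. The total is 228.75 minutes.

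| | Start 50 mg/hr | Start 100 mg/hr |
|---|---|---|
| Dose by 30 min | 25 mg | 50 mg |
| Dose by 60 min | 25 + 50 = 75 mg | 50 + 75 = 125 mg |
| Total time | 255 min | 228.75 min |

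Difference in total time: 255 − 228.75 = 26.25 minutes.

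**Where the two texts agree and where they do not**

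| Rate at first-infusion reaction (mg/hr) | Main-body Table 2 start | Appendix 7 start | Compatible? |
|---|---|---|---|
| 50 | 50 | at most 25 | No |
| 100 | 50 | at most 50 | Yes, at 50 |
| 150 | 50 | at most 75 | Yes, at 50 |
| 200 | 50 | at most 100 | Yes, at 50 |
| 250, 300, 350, 400 | 50 | 100 | Defaults differ |

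The cap does not settle the last row. Half of 250, 300, 350 and 400 is 125, 150, 175 and 200 mg/hr, so 50 and 100 both satisfy it. The 50 mg/hr row is a lesser mismatch in the other direction.

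**The case against.** The best defence is that a site can comply with both texts. Because the Appendix 7 rates can be slowed at discretion, a 50 mg/hr start after a reaction above 200 mg/hr breaches neither. One can also read the 100 mg/hr sentence as a deliberate exception to the general return to the initial schedule. The other safeguards apply at any starting rate: premedication, close supervision, stop-or-slow rules, and permanent discontinuation for a Grade 4 or recurrent Grade 3 reaction.

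Most of this stands, and it is why the point is minor. It does not remove the inconsistency. Permission to go slower does not make the written 100 mg/hr default agree with main-body Table 2, and Table 2 contains no exception for high-rate reactions.

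A reader might infer three stronger things that the documents do not support.

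- **That 100 mg/hr is unsafe.** No evidence of this is given. It lies within the half-rate cap. It is also below the 125 to 200 mg/hr at which both texts allow a same-day restart after a reaction at 250 to 400 mg/hr (main-body Table 2: "Resume the infusion at a 50% reduction in rate"; Appendix 7: "the infusion may be restarted at half the rate"). Section 5.1.1 adds that, in the CLL and NHL studies, most patients had no such reactions at later infusions.
- **That the gap is as large as 60 minutes, or 75 against 150 mg by 60 minutes.** Those figures take the 195-minute schedule in Appendix 7 Table 2, with +100 mg/hr steps. Appendix 7 offers that schedule to patients who tolerated the first infusion and sends those with a clinically significant reaction to the initial schedule, with +50 mg/hr steps.
- **That the trial's efficacy result is affected.** The starting rate changes neither the planned dose nor the primary analysis.

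**Conclusion.** The inconsistency is real and minor. For a clinically significant first-infusion reaction above 200 mg/hr, the written default for the second infusion is 50 mg/hr in one place and 100 mg/hr in the other, with no order of precedence in the protocol. The size is a two-fold difference in starting rate, 50 mg more drug in the first hour (125 − 75), and an infusion about 26 minutes shorter. These figures assume that a patient started at 100 mg/hr then follows the +50 mg/hr steps of the initial schedule and that no further reaction interrupts the infusion. The lesser mismatch, after a reaction at 50 mg/hr, is 50 against at most 25 mg/hr.

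The documents do not say how many patients fell into either group. The last infusion was due on Day 182, and SAP Section 1 records that the Week 52 and Week 104 reports are already issued. No patient's dosing in this trial can now change; what remains is the clarity of the protocol text and any reuse of the appendix.

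**What to change.** In Appendix 7, delete the sentence that starts the second infusion at 100 mg/hr, and limit the next paragraph's 100 mg/hr start to patients who tolerated the prior infusion well. In both main-body Table 2 and Appendix 7, state the same rule: after an infusion-related reaction at the prior infusion, start the next one at 50 mg/hr on the first-infusion schedule, or lower at the investigator's discretion, including where the half-rate cap requires it. This uses the main-body trigger (any reaction), which is wider than Appendix 7's clinically significant reaction; the sponsor should confirm that this is intended.

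The cost is a text change and, in any reuse, about 26 more minutes of infusion for patients who reacted above 200 mg/hr. Patients who reacted at 50 mg/hr and start lower would also have a longer infusion. Its length cannot be fixed from the documents, because neither text says how long a sub-50 mg/hr starting rate is to be held.
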